4.3 Withdrawal of Subjects from Study Treatment and/or Study

Permanent discontinuation of Durvalumab

An individual subject will not receive any further investigational product if any of the following occur in the subject in question:

1. Withdrawal of consent or lost to follow-up
2. Adverse event that, in the opinion of the investigator or the sponsor, contraindicates further dosing. Patients with grade 3 toxicity at least possibly related to study drug will discontinue durvalumab. Patients with prolonged grade 2 toxicity or who require dose delays for more than 2 weeks or require prolonged steroid use will discontinue durvalumab.
3. Subject is determined to have met one or more of the exclusion criteria for study participation at study entry and continuing investigational therapy might constitute a safety risk
4. Pregnancy or intent to become pregnant
5. Any AE that meets criteria for discontinuation as defined in Appendix A
6. Grade ≥ 3 infusion reaction
7. Subject noncompliance that, in the opinion of the investigator or sponsor, warrants withdrawal; eg, refusal to adhere to scheduled visits
8. Initiation of alternative anticancer therapy including another investigational agent
9. Confirmation of PD and investigator determination that the subject is no longer benefiting from treatment with durvalumab

Subjects who are permanently discontinued from further receipt of investigational product, regardless of the reason (withdrawal of consent, due to an AE, other), will be identified as having permanently discontinued treatment.

Subjects who are permanently discontinued from receiving investigational product will be followed for safety per Section 10.3.1 and Appendix C or D, including the collection of any protocol-specified blood specimens, unless consent is withdrawn or the subject is lost to

Clinical Study Protocol

Drug Substance Durvalumab (Medi4736)

Study Number MCC 18788/MCC18788/ESR-15-11326

Edition Number 1.9.4

Date 10/08/2018

follow-up or enrolled I another clinical study. All subjects will be followed for survival. Subjects who decline to return to the site for evaluations will be offered follow-up by phone every 3 months as an alternative.

Withdrawal of consent

If consent is withdrawn, the subject will not receive any further investigational product or further study observation.

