5.1.2 Durvalumab Doses and treatment regimens

Treatment with fixed dose durvalumab at 1500 mg Q4W durvalumab (equivalent to 20 mg/kg Q4W, based on an average body WT of 75 kg) commences on Day 1 following confirmation of eligibility into the study and continues on a Q4W schedule for a maximum duration of treatment of 12 months (maximum of 13 doses). Study treatment should be discontinued prior to 12 months if there is confirmed PD (unless the investigator considers the subject to continue to receive benefit from treatment), initiation of alternative cancer therapy,

unacceptable toxicity, withdrawal of consent, or if other reasons to discontinue study treatment occur.

Subjects who have a dose interruption due to toxicity at any point in the first 12 months of treatment may resume treatment and complete the 12-month treatment period.

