6.3 Durvalumab Dose Modification and Toxicity Management

For adverse events (AEs) that are considered at least partly due to administration of durvalumab, the following dose adjustment guidance may be applied:

- Treat each of the toxicities with maximum supportive care (including holding the agent suspected of causing the toxicity where required).
- If the symptoms promptly resolve with supportive care, consideration should be given to continuing the same dose of durvalumab along with appropriate continuing supportive care. If medically appropriate, dose modifications are permitted for durvalumab (see below).
- All dose modifications should be documented with clear reasoning and documentation of the approach taken.

Clinical Study Protocol

Drug Substance Durvalumab (Medi4736)

Study Number MCC 18788/MCC18788/ESR-15-11326

Edition Number 1.9.4

Date **10/08/2018**

In addition, there are certain circumstances in which durvalumab should be permanently discontinued. These circumstances include but not limited to grade 3 toxicity at least possibly related to durvalumab; and prolonged grade 2 toxicity requiring dose delays for more than 2 weeks or requiring prolonged steroid use will discontinue durvalumab.

Following the first dose of durvalumab, subsequent administration of durvalumab can be modified based on toxicities observed (see Table 1, 2, and 3 in Appendix A). Dose reductions are not permitted.

Based on the mechanism of action of durvalumab leading to T-cell activation and proliferation, there is the possibility of observing immune related Adverse Events (irAEs) during the conduct of this study. Potential irAEs include immune-mediated enterocolitis, dermatitis, hepatitis, and endocrinopathies. Subjects should be monitored for signs and symptoms of irAEs. In the absence of an alternate etiology (e.g., infection or PD) signs or symptoms of enterocolitis, dermatitis, hepatitis, and endocrinopathy should be considered to be immune-related.

Dose modification recommendations and toxicity management guidelines for immune-mediated reactions, for infusion-related reactions, and for non-immune-mediated reactions are detailed in Tables 1, 2, and 3 respectively.

In addition, management guidelines for adverse events of special interest (AESIs) are detailed in Section 10.1.3. All toxicities will be graded according to NCI CTCAE V4.03.

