
Drug administration modifications of study drug/study regimen will be made to manage potential immune-related AEs based on severity of treatment-emergent toxicities graded per NCI CTCAE v4.03.
 
In addition to the criteria for permanent discontinuation of study drug/study regimen based on CTC grade/severity (table below), permanently discontinue study drug/study regimen for the following conditions:
 
• Inability to reduce corticosteroid to a dose of ≤ 10 mg of prednisone per day (or equivalent) within 12 weeks after last dose of study drug/study regimen• Recurrence of a previously experienced Grade 3 treatment-related AE following resumption of dosing 
Grade 1 No dose modification
 
Grade 2 Hold study drug/study regimen dose until Grade 2 resolution to Grade ≤ 1. If toxicity worsens, then treat as Grade 3 or Grade 4. Study drug/study regimen can be resumed once event stabilizes to Grade ≤ 1 after completion of steroid taper. Patients with endocrinopathies who may require prolonged or continued steroid replacement can be retreated with study drug/study regimen on the following conditions:
1. The event stabilizes and is controlled.2. The patient is clinically stable as per Investigator or treating physician's clinical judgement.3. Doses of prednisone are at ≤ 10 mg/day or equivalent.
 
Grade 3 Depending on the individual toxicity, study drug/study regimen may be permanently
	
It is recommended that management of immune-mediated adverse events (imAEs) follows the guidelines presented in this table:
 
– It is possible that events with an inflammatory or immune mediated mechanism could occur in nearly all organs, some of them not noted specifically in these guidelines.– Whether specific immune-mediated events (and/or laboratory indicators of such events) are noted in these guidelines or not, patients should be thoroughly evaluated to rule out any alternative etiology (e.g., disease progression, concomitant medications, and infections) to a possible immune-mediated event. In the absence of a clear alternative etiology, all such events should be managed as if they were immune related. General recommendations follow.– Symptomatic and topical therapy should be considered for low-grade (Grade 1 or 2, unless otherwise specified) events.– For persistent (>3 to 5 days) low-grade (Grade 2) or severe (Grade ≥ 3) events, promptly start prednisone 1 to 2 mg/kg/day PO or IV equivalent.– Some events with high likelihood for morbidity and/or mortality – e.g., myo-carditis, or other similar events even if they are not currently noted in the guidelines – should progress rapidly to high dose IV corticosteroids (methylprednisolone at 2 to 4 mg/kg/day) even if the event is Grade 2, and if clinical suspicion is high and/or there has been clinical confirmation. Consider, as necessary, discussing with the study physician, and promptly pursue specialist consultation.– If symptoms recur or worsen during corticosteroid tapering (28 days of taper), increase the corticosteroid dose (prednisone dose [e.g., up to 2 to 4 mg/kg/day PO or IV equivalent]) until stabilization or improvement of symptoms, then resume corticosteroid tapering at a slower rate (>28 days of taper).– More potent immunosuppressives such as TNF inhibitors (e.g., infliximab) (also refer to the individual sections of the imAEs for specific type of immunosuppressive) should be considered for events not responding to systemic steroids.

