
Dosing Modification and Toxicity Management Guidelines for Immune-Mediated, Infusion-Related, and Non-Immune-Mediated Reactions (MEDI4736 Monotherapy or Combination Therapy With Tremelimumab or Tremelimumab Monotherapy) 1 November 2017 Version

General Considerations

Dose Modifications		Toxicity Management

discontinued. Please refer to guidelines below.
 
Grade 4 Permanently discontinue study drug/study regimen.
 
Note: For Grade ≥ 3 asymptomatic amylase or lipase levels, hold study drug/study regimen, and if complete work up shows no evidence of pancreatitis, study drug/study regimen may be continued or resumed.
 
Note: Study drug/study regimen should be permanently discontinued in Grade 3 events with high likelihood for morbidity and/or mortality – e.g., myocarditis, or other similar events even if they are not currently noted in the guidelines. Similarly, consider whether study drug/study regimen should be permanently discontinued in Grade 2 events with high likelihood for morbidity and/or mortality – e.g., myocarditis, or other similar events even if they are not currently noted in the guidelines – when they do not rapidly improve to Grade < 1 upon treatment with systemic steroids and following full taper
 
Note: There are some exceptions to permanent discontinuation of study drug for Grade 4 events (i.e., hyperthyroidism, hypothyroidism, Type 1 diabetes mellitus).
		
Progression to use of more potent immunosuppressives should proceed more rapidly in events with high likelihood for morbidity and/or mortality – e.g., myocarditis, or other similar events even if they are not currently noted in the guidelines – when these events are not responding to systemic steroids.
 
With long-term steroid and other immunosuppressive use, consider need for Pneumocystis jirovecii pneumonia (PJP, formerly known as Pneumocystis carinii pneumonia) prophylaxis, gastrointestinal protection, and glucose monitoring.Discontinuation of study drug/study regimen is not mandated for Grade 3/Grade 4 inflammatory reactions attributed to local tumor response (e.g., inflammatory reaction at sites of metastatic disease and lymph nodes). Continuation of study drug/study regimen in this situation should be based upon a benefit-risk analysis for that patient.

AE Adverse event; CTC Common Toxicity Criteria; CTCAE Common Terminology Criteria for Adverse Events; imAE

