Severity Grade of the Event (NCI CTCAE version 4.03)	Dose Modifications	Toxicity Management
Any Grade	General Guidance	For Any Grade: 
– Manage per institutional standard at the discretion of investigator.– Monitor patients for signs and symptoms of infusion-related reactions (e.g., fever and/or shaking chills, flushing and/or itching, alterations in heart rate and blood pressure, dyspnea or chest discomfort, or skin rashes) and anaphylaxis (e.g., generalized urticaria, angioedema, wheezing, hypotension, or tachycardia).
Grade 1 or 2	For Grade 1: 
The infusion rate of study drug/study regimen may be decreased by 50% or temporarily interrupted until resolution of the event.
 For Grade 2: 
The infusion rate of study drug/study regimen may be decreased 50% or temporarily interrupted until resolution of the event.
 
Subsequent infusions may be given at 50% of the initial infusion rate.
	For Grade 1 or 2: 
– Acetaminophen and/or antihistamines may be administered per institutional standard at the discretion of the investigator.– Consider premedication per institutional standard prior to subsequent doses.– Steroids should not be used for routine premedication of Grade ≤ 2 infusion reactions.
Grade 3 or 4	For Grade 3 or 4: 
Permanently discontinue study drug/study regimen.
	For Grade 3 or 4: 
– Manage severe infusion-related reactions per institutional standards (e.g., IM epinephrine, followed by IV diphenhydramine and ranitidine, and IV glucocorticoid).

CTCAE Common Terminology Criteria for Adverse Events; IM intramuscular; IV intravenous; NCI National Cancer Institute.

Clinical Study Protocol

Drug Substance Durvalumab (Medi4736)

Study Number MCC 18788/MCC18788/ESR-15-11326

Edition Number 1.9.4

Date **10/08/2018**

Non-Immune-Mediated Reactions

Severity Grade of the Event (NCI CTCAE version 4.03)	Dose Modifications	Toxicity Management
Any Grade	Note: Dose modifications are not required for AEs not deemed to be related to study treatment (i.e., events due to underlying disease) or for laboratory abnormalities not deemed to be clinically significant.	Treat accordingly, as per institutional standard.
Grade 1	No dose modifications.	Treat accordingly, as per institutional standard.
Grade 2	Hold study drug/study regimen until resolution to \leq Grade 1 or baseline.	Treat accordingly, as per institutional standard.

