Grade 3	Hold study drug/study regimen until resolution to \leq Grade 1 or baseline. For AEs that downgrade to \leq Grade 2 within 7 days or resolve to \leq Grade 1 or baseline within 14 days, resume study drug/study regimen administration. Otherwise, discontinue study drug/study regimen.	Treat accordingly, as per institutional standard.
Grade 4	Discontinue study drug/study regimen (Note: For Grade 4 labs, decision to discontinue should be based on accompanying clinical signs/symptoms, the Investigator's clinical judgment, and consultation with the Sponsor.).	Treat accordingly, as per institutional standard.

Note: As applicable, for early phase studies, the following sentence may be added: "Any event greater than or equal to Grade 2, please discuss with Study Physician."

AE Adverse event; CTCAE Common Terminology Criteria for Adverse Events; NCI National Cancer Institute.

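### Appendix A tells sites to resume durvalumab after a related, recovering non-immune Grade 3 event, which Sections 4.3 and 6.3 say must end treatment

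*Combined protocol and SAP*

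**What the plan says.** **Body text.** Section 4.3 lists the grounds for permanent discontinuation, and its opening sentence makes any one of them sufficient. Item 2 includes: "Patients with grade 3 toxicity at least possibly related to study drug will discontinue durvalumab". Item 5 adds events that meet the discontinuation criteria in Appendix A. Section 6.3 repeats the Grade 3 rule among the circumstances for a permanent stop: "These circumstances include but not limited to grade 3 toxicity at least possibly related to durvalumab". Neither section makes an exception for an event that resolves.

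**Link to the appendix.** Directly after that list, Section 6.3 says that "subsequent administration of durvalumab can be modified based on toxicities observed (see Table 1, 2, and 3 in Appendix A".

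**Appendix A, Non-Immune-Mediated Reactions.** The note for any grade says "Dose modifications are not required for AEs not deemed to be related to study treatment". The Grade 3 cell says to hold the drug. It then allows a restart if the event falls to Grade 2 or lower within 7 days, or under a second condition: "Grade 1 or baseline within 14 days, resume study drug/study regimen administration. Otherwise, discontinue study drug/study regimen".

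**Appendix A, General Considerations.** One trigger for a permanent stop is "Recurrence of a previously experienced Grade 3 treatment-related AE following resumption of dosing". For Grade 3 or higher amylase or lipase without symptoms, the drug is held, and "if complete work up shows no evidence of pancreatitis, study drug/study regimen may be continued or resumed".

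**Section 5.1.2.** "Subjects who have a dose interruption due to toxicity at any point in the first 12 months of treatment may resume treatment", with no limit on grade.

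**The concern.** The same event gets opposite instructions depending on the page a site opens. A site working from the table would re-dose a patient whom Sections 4.3 and 6.3 take off the drug. With two or three centers, the same event could be handled differently from one center to the next. That is mainly a patient-safety and consistency matter.

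There is a secondary statistical effect. The efficacy analysis set (Section 11.1.2) requires at least six infusions, and Section 6.1 calls subjects with fewer than six not evaluable. The rule a site applies can therefore decide whether a subject counts in the efficacy set.

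**Working it through.** The protocol gives no figure on this point to reproduce. The check compares texts and then estimates how often the conflict could arise.

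**1. Do the rules cover the same events?** Sections 4.3 and 6.3 apply to Grade 3 toxicity at least possibly related to durvalumab. The non-immune table needs no dose change for unrelated events, so its Grade 3 hold-and-resume instruction operates on related events. The populations overlap.

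**2. Test case.** A possibly related, non-immune Grade 3 event resolves to Grade 1 by day 10.
- Section 4.3 item 2 and Section 6.3: stop permanently.
- Appendix A cell: resume, because Grade 1 was reached within 14 days.

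If the event is still Grade 3 at day 14, both texts stop the drug. The conflict is confined to events that recover in time. The cell also says to hold until Grade 1 or baseline while allowing a restart at Grade 2 within 7 days; this smaller ambiguity disappears once the cell is replaced.

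**3. How far does the mismatch extend?** Leaving out the block for hepatocellular carcinoma patients, Appendix A has 12 reaction types with a Grade 3 rule (10 immune-mediated, infusion-related, non-immune).

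| Grade 3 rule in Appendix A | Reaction types | Count |
|---|---|---|
| Can continue or resume | Colitis, hepatitis, rash, endocrinopathy, neurotoxicity, peripheral neuromotor syndromes, myositis, non-immune | 7 + 1 = 8 |
| Permanent stop | Pneumonitis, nephritis, myocarditis, infusion-related | 4 |

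The amylase/lipase note is a further place where the drug may continue or resume.

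**4. Do other grades have the same problem?**
- Grade 4: Appendix A lets the drug continue or resume in Grade 4 endocrinopathy. If the body text prevailed at Grade 3 only, a related Grade 3 endocrinopathy would end treatment while a Grade 4 one need not.
- Grade 2: Section 4.3 stops the drug for prolonged toxicity, delays beyond 2 weeks or prolonged steroid use. Several Appendix A rows resume after a Grade 2 event once a steroid taper of at least 28 days is complete. That can breach the Section 4.3 limits.

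**5. How many subjects?** Section 1.2.2 reports that in study 1108 65 of 694 subjects had a treatment-related event of Grade 3 or higher. Assume that rate applies here.
- Rate: p = 65/694 = 0.0937 (exact 95% CI 0.0730 to 0.1178).
- Expected subjects per 34 treated: 34 × 0.0937 = 3.2 (34 × 0.0730 = 2.5 to 34 × 0.1178 = 4.0).
- Chance of 4 or more, X ~ Binomial(34, p): 1 − [P(0) + P(1) + P(2) + P(3)] = 1 − (0.035 + 0.124 + 0.212 + 0.233) = 0.40.

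The count includes immune-mediated and Grade 4 to 5 events, so the expected number governed by the non-immune Grade 3 cell is lower. The documents do not give it.

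**6. Effect on the analysis sets.** Infusions fall at weeks 0, 4, 8, 12, 16 and 20, so without delays the sixth is at week 20. A subject stopped before then has fewer than six doses and is outside the efficacy set. Section 11.1.2 also plans an intention-to-treat analysis of subjects with at least one dose and the month 6 mapping biopsy. The same subject stays in that analysis if biopsied.

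**The case against.** The strongest reply is that Section 4.3 already gives the answer. Any listed ground ends dosing, item 2 is such a ground, and item 5 uses Appendix A only to add reasons for stopping. Nothing in Section 4.3 lets the appendix cancel item 2. This stands: a reader might infer that sites are left with no rule, and the documents do not support that. What remains is an operative table carrying the contrary instruction. Section 6.3 sends sites to it, and its general rules presuppose re-dosing after a related Grade 3 event. Section 6.3 also asks investigators to consider continuing the same dose when symptoms resolve promptly.

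Second, Appendix A is plainly a general guideline. It covers tremelimumab, pediatric patients and hepatocellular carcinoma, and a stricter study-specific rule alongside such a guideline is ordinary. That explains the mismatch but does not cure it, because the protocol adopts the tables without saying that its own rule overrides them.

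Third, Section 5.1.2 is weak evidence of conflict. It concerns interruptions, and the preceding paragraph requires discontinuation for unacceptable toxicity. It can be read as covering Grade 2 holds only. That is fair, and the point does not depend on it.

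**Conclusion.** The point holds as an internal inconsistency. The non-immune Grade 3 cell is wrong against Sections 4.3 and 6.3, and seven immune-mediated rows and the amylase/lipase note share the mismatch. The body text favours stopping, but no sentence says that it prevails.

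The size is small. It rests on carrying over a rate from advanced solid tumors treated at 10 mg/kg every 2 weeks, whereas this trial treats carcinoma in situ at 1500 mg every 4 weeks. Two stronger readings should be avoided.
- A reader might take 3.2 of 34 as an upper limit. It is an expected count, and four or more affected subjects would occur with probability 0.40 at that rate. Also, 34 is the evaluable target. Sections 4.4 and 6.1 replace subjects withdrawn before the month 6 biopsy, so more than 34 may be treated.
- A reader might infer that a subject stopped early drops out of the efficacy results altogether. Only the six-dose efficacy set loses that subject; the intention-to-treat analysis does not, provided the month 6 biopsy is done.

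The documents do not give the share of events arising before the sixth dose, so the effect on the efficacy set cannot be quantified.

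**What to change.** 1. Replace the Appendix A non-immune Grade 3 cell with:

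> Permanently discontinue durvalumab for any Grade 3 event at least possibly related to study drug (Sections 4.3 and 6.3).

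2. Add to Section 6.3 and to the head of Appendix A:

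> Where Appendix A would allow durvalumab to continue or resume and Section 4.3 or 6.3 requires discontinuation, Sections 4.3 and 6.3 prevail; this covers related toxicity of Grade 3 or higher, and Grade 2 toxicity that is prolonged, delays dosing by more than 2 weeks or needs prolonged steroids.

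3. If the sponsor wants exceptions, such as endocrinopathy managed with hormone replacement or asymptomatic amylase or lipase elevation, write them into Sections 4.3 and 6.3. That is a clinical choice for the sponsor.

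The cost is one table cell and one sentence placed twice. Sites lose the more lenient Appendix A options unless the sponsor keeps them under step 3. At Grade 3 nothing is added to what the body text already requires. Sections 4.3 and 6.3 name Grade 3 only, so the sentence makes explicit that Grade 4 is included; the sponsor should confirm this. The Grade 2 wording follows Section 4.3, which Section 6.3 phrases slightly differently.
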